8.3.2 Secondary endpoints

The secondary endpoints will also be assessed on their strength of correlation as well as the magnitude of rate of occurrence of VF/VT and arrhythmic death in the subjects with an LVEF greater than 35%.

8.4 Statistical Methods

For primary, secondary, and safety endpoints, descriptive statistics and qualitative analysis will be performed as appropriate.

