2.1 Primary Objective(s)

The following primary objectives will be evaluated during the wear period of the μ Cor device:

- 2.1.1 To identify correlations between μ Cor measurements (thoracic fluid index, cardiac rhythm, respiration rate, physical activity, and posture) with occurrences of heart failure related clinical events occurring within 90 days of hospital discharge for acute decompensated heart failure.

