3.2 Primary Study Endpoints

The primary endpoints that will be evaluated at the end of the study include:

3.2.1 Correlation of μ Cor readings (thoracic fluid index, cardiac rhythm, respiration rate, posture, and physical activity) to clinical events

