8.1 Sample Size and Power Calculation

The sample size was chosen to answer the primary and secondary objectives. We expect a 50/50 distribution between patients enrolled with an LVEF less than 35% and an LVEF greater than 35%. After the 200th patient is enrolled, we will conduct an interim analysis to confirm the LVEF distribution.

The first 200 patients will generate a convenience sample of heart failure related clinical events. Assuming a 20% event rate within the first 30 days in patients with reduced LVEF, we estimate that we will observe at least 25-30 heart failure related events among patients with reduced EF through the length of the 90 day study period (accounting for not all patients reaching completion).

We believe that 25-30 heart failure related events will be enough events to draw meaningful correlations among μ Cor device measurements and heart failure related episodes.

Following the interim analysis, the additional 300 subjects will further generate heart failure related clinical events to answer the primary objective and be monitored for VT/VF arrhythmic events to answer the secondary objectives.

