8.3 Endpoint Assessment

8.3.1 Primary endpoint

The first primary endpoint will be assessed by the strength of the correlation between μ Cor device readings and heart failure related clinical events.

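### The primary endpoint is judged on the descriptive strength of correlation for five readings, with no interval, chance benchmark or allowance for five readings, so the plan gives no way to tell a chance correlation from a real one

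*Combined protocol and SAP*

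**What the plan says.** Section 2.1 sets the primary objective: "To identify correlations between μ Cor measurements (thoracic fluid index, cardiac rhythm, respiration rate, physical activity, and posture". The outcome against which these readings are set is any clinical event due to heart failure in the 90 days after discharge. Section 3.2 lists the same five readings as the primary endpoint. Section 8.3.1 says the endpoint will be "assessed by the strength of the correlation between μ Cor device readings and heart failure related clinical events".

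The method is the single sentence of section 8.4: "For primary, secondary, and safety endpoints, descriptive statistics and qualitative analysis will be performed as appropriate". Section 8.5, on additional analysis, reads NA. The document states no coefficient, confidence interval, alpha, null comparison, multiplicity rule or minimum correlation of interest.

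On the amount of information needed, section 8.1 states: "We believe that 25-30 heart failure related events will be enough events to draw meaningful correlations". The one numeric trigger linked to the results, in section 8.7, is fewer than 5 heart failure events at the interim. That counts events and sets no standard for a correlation.

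**The concern.** A sample correlation is almost never exactly zero, and the largest of five is larger than a typical one. If readings are judged by size with nothing to compare against, the reader of the final report cannot know whether the leading reading tracks heart failure events or is the luckiest of five that do not. This holds for whatever measure of association is eventually chosen.

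It is more than a matter of presentation. The plan calls this the primary endpoint, uses it to justify the event count in section 8.1, and schedules an assessment of it in section 8.7 when 200 subjects have completed wear. At that look the event count is small and chance correlations are at their largest.

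**Working it through.** **The plan's own figure.** Section 8.1 expects at least 25-30 events in reduced-LVEF patients among the first 200 subjects.
- Reduced-LVEF subjects: 200 × 0.5 = 100.
- Events by day 30: 100 × 0.20 = 20.
- Events by day 90 at constant hazard, no losses: 100 × (1 − 0.8³) = 48.8.
- The stated 25-30 is 25/48.8 = 51% to 30/48.8 = 61% of that. Losses are mentioned but not quantified, so the figure is plausible as a floor but cannot be reproduced.

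I take 27 events as a mid-range value. Section 8.1 attaches the 25-30 to the reduced-LVEF patients (about 100), while section 8.7 attaches it to all 200, so I use both denominators. For the full study I scale 27/200 to 500 subjects: 67.5, taken as 68. This is an assumption.

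**Other assumptions, not in the documents.** One summary value per reading per subject, each subject with or without an event, five independent readings analysed one by one, and no true association.

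**Largest of five by chance.** For a cut-off c, t = c × √((N − 2)/(1 − c²)), p is the two-sided tail probability on N − 2 degrees of freedom, and P(largest |r| ≥ c) = 1 − (1 − p)⁵. Setting this to 0.50 and 0.05 gives the median and the 95th percentile.

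**A real effect for comparison.** A true difference of d = 0.5 SD between subjects with and without events, with event fraction q, gives r = d√(q(1 − q)) / √(1 + d²q(1 − q)). At 27 in 100, q(1 − q) = 0.1971, so r = 0.222/1.024 = 0.217.

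**Chance that this effect exceeds the null 95th percentile.** By Fisher's z: Φ[(atanh r − atanh c) × √(N − 3)]. At N = 500: (atanh 0.169 − atanh 0.115) × √497 ≈ 1.23, which gives 89%.

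| Subjects / events | Median largest null abs(r) | 95th percentile | r for a 0.5-SD effect | Chance effect exceeds 95th percentile |
|---|---|---|---|---|
| 100 / 27 | 0.153 | 0.256 | 0.217 | about 34% |
| 200 / 27 | 0.108 | 0.181 | 0.168 | about 43% |
| 500 / 68 | 0.068 | 0.115 | 0.169 | about 89% |

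Simulation with a fixed event vector agrees: null median and 95th percentile of 0.152 and 0.258, 0.107 and 0.180, and 0.068 and 0.115 in the three rows, and 35%, 43% and 89% in the last column.

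**If a size cut-off were used.** The plan sets none, so these are illustrations. P(largest null |r| ≥ 0.10) is 86%, 58% and 12% at N = 100, 200 and 500. For 0.15 it is 52%, 16% and 0.4%.

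**If unadjusted 5% tests were used.** 1 − 0.95⁵ = 22.6% chance of flagging at least one useless reading.

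**Sensitivity.** If the readings correlate with each other at 0.6, the figures for 0.10 fall to about 74%, 44% and 9%, and the 22.6% falls to 16-17%. Daily readings analysed without allowing for clustering, or several summaries per reading, would push the chance rates up.

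**The case against.** The study is observational and descriptive. The plan states no hypothesis, cut-off or yes/no call, and it does not say that the strongest reading will be singled out. It lists five readings without saying whether they are analysed one by one or combined. Descriptive statistics could include intervals, since section 8.4 does not rule them out. The primary endpoint is evaluated at the end of the study, and section 8.1 says the further 300 subjects add events for it, so 100 or 200 subjects is not the main analysis. The device transmits daily, so one value per subject is a simplification.

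Much of this stands, and it limits the point. A reader might infer that useless readings will usually produce what looks like a correlation. The documents do not support that: they set no size that counts, and at 500 subjects the chance of reaching |r| ≥ 0.10 is 12%. A reader might also infer that the study cannot separate a real reading from the luckiest of five. That fails too, because at the planned size a half-SD effect clears the chance benchmark about 89% of the time under the stated assumptions.

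The objection does not supply the missing step. Separate analysis is the natural reading of a plural list with no combined index described. Permitting intervals is not the same as planning them. If the aim is only exploratory, the plan should say so, but section 8.1 instead asserts that 25-30 events suffice.

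**Conclusion.** The point holds as a gap in the reporting rule. Followed as written, the plan gives no means of distinguishing a chance correlation from a real one among the five readings.

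The gap is most serious at 25-30 events, where a half-SD effect lies below the null 95th percentile with either denominator. At full size the data are adequate for an effect of that size and only the rule is missing. Testing each reading at 5% without adjustment would not close the gap, since it would flag a useless reading in up to about 23% of null trials.

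These numbers rest on one value per subject, independent readings and an assumed 68 events in 500. They show the scale of the problem and do not estimate this study's error rate. The absence of an interval, benchmark and multiplicity rule is read directly from the text. A change should be made, ideally before any reading is set against events.

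**What to change.** In section 8.4, name the association measure or model for each reading and add wording to this effect for the primary endpoint:

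*Each of the five reading-event associations will be reported with a 95% confidence interval that respects clustering within subject, with the subject as the resampling unit. An association will be called identified only if it remains significant at a two-sided familywise 5% level across the five readings, using Holm's procedure or a max-statistic permutation of subjects within patch-position and region strata that accounts for wear time. Any other association will be labelled exploratory.*

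The strata are needed because section 8.2 ties patch position to enrolment order and country. Wear time matters because it differs between subjects, so permuting freely across all subjects would not be valid.

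In section 8.1, qualify the sentence on 25-30 events so that results based on that many events are described as exploratory. Reconcile sections 8.1 and 8.7 on whether the 25-30 refers to reduced-LVEF patients or to all 200.

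The cost is plan wording and a short program, with no new data, visits or subjects. The downside is that a weak but real correlation may be reported as exploratory.

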8.5 Additional Statistical Analysis

NA

8.6 Handling Missing Data

As with any clinical study, missing data are to be expected during this study.

8.6.1 Sources of Missing Data

- 8.6.1.1 Medical records not available
- 8.6.1.2 Subjects who are lost to follow up
- 8.6.1.3 Device error
- 8.6.1.4 Missed phone calls
- 8.6.1.5 Missed visits

8.6.2 Preventing Missing Data

8.6.2.1 All attempts to maintain contact with the subject should be made by study personnel to assure that lost to follow up subjects are kept to a minimum. This may involve telephone calls. Multiple phone numbers/contacts for each subjects should be collected. Multiple reminders of upcoming visits should be made.

8.6.2.2 Reasonable windows of time (within 2 days for phone calls and 5 days for clinic visits) have been employed.

8.6.2.3 Routine site monitoring with data verification will occur throughout the study.

8.6.3 Handling missing data

8.6.3.1 Missing data will not be replaced by any algorithm.

8.6.3.2 If a subject is missing more than 50% of data, the subject's data will not be included in the analysis.

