3.4 Safety Endpoints

All adverse events related to the use of the μ Cor will be used to assess safety during the study.

4 Study Subject

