6.4 Long-term Clinical Outcome Assessment

The subject will receive a follow up phone call 6 months and 1 year from the enrollment date to assess for mortality status, heart failure related clinical events that have occurred since the end of μ Cor wear, and any health care utilization that has occurred since the end of μ Cor wear. A chart review will be performed during both of these calls as well. Subjects will answer mailed heart failure questionnaires and mail the questionnaires back to the site.

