6.5 Study Procedures Flowchart (or Table)

Summary of the activities and procedures to be followed at each visit is as described below (Table 1).

	Visit 1	Visit 2	Visit 3	Visit 4	6 Months	1 Year
Eligibility Screening	X					
Consent	X					
Enrollment	X					
Physical Assessment	X	X	X	X		
μ Cor Setup	X					
EF Documentation*	X					
HF Event Documentation	X	X	X	X	X	X
Weight Documentation	X	X	X	X	X	X
HF Questionnaires	X	X	X	X	X	X

Table 1: Visit Procedure List (*All EF measurements will be documented if clinically indicated)

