8.7 Futility Analysis

The study will be considered ineffective if the interim analysis determine the study will be unsuccessful enrolling the required number of subjects (≥ 1 subject per center-month), or if occurrence of the primary endpoint is deemed insufficient to successfully complete the study with the planned number of subjects.

Both an interim and futility analysis will be performed once the 200th subject has completed wear time. Primary and secondary endpoints will be assessed. With 200 patients completing wear time, it is expected that there would be about 25 -30 heart failure related clinical events. If during the interim and futility assessments, there are less than 5 heart failure events, a protocol change will be considered.

9 Health Economic Evaluation

The Kansas City Heart Failure Questionnaire will be given to the subjects at all monthly clinic visits. We will develop a model to examine the costs and benefits of using uCor. The model will use data from our review of monthly collected questionnaire, heart failure event, as well as data from recognized sources (e.g. national published data, finance department of hospital), and experts' advice

10 Safety and Adverse Device Effects

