10.1.1 Foreseeable Adverse Device Effects with Study Device

The most common foreseeable adverse event is skin rash. This is expected to occur in a small minority of patients.

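### Section 8.6.3.2 drops whole subjects for more than 50% missing data without defining the data, period or endpoints, so subjects with known outcomes can be excluded

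*Combined protocol and SAP*

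**What the plan says.** Section 8.6.3 contains two rules. Missing values are not imputed, and "If a subject is missing more than 50% of data, the subject's data will not be included in the analysis". No analysis sets are defined elsewhere, so these are the only operative rules for missing data.

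Three places bear on how far the second rule reaches:

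- Section 8.6.1 lists the sources of missing data. Beside device error it names unavailable medical records, missed calls, missed visits and "Subjects who are lost to follow up". The word *data* is therefore not clearly device data.
- Section 8.4 covers all endpoint classes in one sentence: "For primary, secondary, and safety endpoints, descriptive statistics and qualitative analysis will be performed as appropriate". Nothing ties the exclusion to the primary analysis alone.
- Sections 2.1 and 2.2 give evaluation periods for the objectives (the wear period and the entire study), but neither is made the base for the 50%.

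Other sections say what is to be collected and used. Section 3.3.7 makes mortality, heart failure events and health care use at 6 months and 1 year a secondary endpoint. Section 6.4 obtains these by telephone, timed from enrolment, and adds: "A chart review will be performed during both of these calls as well". Section 2.3 sets out to document every adverse event caused by the device, and section 3.4 says that all such events "will be used to assess safety during the study". Section 5.4.2 keeps withdrawn subjects' data for analysis, with deletion only if consent to use the data is withdrawn.

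**The concern.** The rule acts on the whole subject and depends on what happens after enrolment. Early stopping of wear is one way to become incomplete, and the design adds to it, because section 3.1.1 holds no further clinic visits once wear has stopped. Yet the long-term outcomes of the same subject are sought independently of wear. If the rule reaches the secondary analyses, subjects with a known death, readmission or heart failure event can be left out of the rates. So can subjects whose VT/VF was recorded while they wore the device.

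The safety analysis has a similar problem. Section 10.1.1 says: "The most common foreseeable adverse event is skin rash". A subject who stops for good because of such a reaction could meet the 50% criterion, although sections 2.3 and 3.4 want every such event counted. No base is fixed in the documents, so nothing prevents it from being settled once the data are known.

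**Working it through.** **1. The plan's own figures.** The plan gives no number for subjects expected to be excluded. The nearest figure is the 25 to 30 heart failure events. From section 8.1:

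- Reduced-LVEF subjects among the first 200: 200 × 0.5 = 100.
- Events by day 30: 100 × 0.20 = 20.
- Events by day 90 at constant risk: 100 × (1 − 0.8³) = 48.8.
- Share that must be observed to give 25 to 30: 25/48.8 = 51% to 30/48.8 = 61%.

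The allowance for non-completion is not stated, so the figure is compatible with its inputs but cannot be reproduced exactly. It is not disputed here. Section 8.1 places these events among reduced-LVEF subjects, while section 8.7 gives the same number without that limit ("With 200 patients completing wear time, it is expected that there would be about" 25 to 30). I therefore do not turn it into a rate per 200.

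**2. Does the base matter?** Inputs are 90 days of wear (section 3.1.1), the six contacts and 27 marked cells of Table 1 (section 6.5), and no visits after wear stops (section 3.1.1). Take a subject who completes both late contacts. Exclusion requires more than 50% missing.

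| Base | Wear stops day 40 | Wear stops day 20 |
|---|---|---|
| 90 wear days | 50/90 = 56%, dropped | 70/90 = 78%, dropped |
| Visits 1 to 4 | 2/4 = 50%, kept | 3/4 = 75%, dropped |
| Six Table 1 contacts | 2/6 = 33%, kept | 3/6 = 50%, kept |
| All 27 Table 1 cells | 8/27 = 30%, kept | 12/27 = 44%, kept |
| 23 cells, without eligibility, consent, enrolment and setup | 8/23 = 35%, kept | 12/23 = 52%, dropped |
| Only contacts still due after wear stops | 0/4 = 0%, kept | 0/3 = 0%, kept |

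Visits 3 and 4 carry four cells each, hence 8. Visits 2 to 4 carry 12. The last row treats a visit that is no longer scheduled as not missed. On the wear-day base, every permanent stop before day 45 leads to exclusion.

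**3. Can a dropped subject have known outcomes?** Yes. In both columns the 6-month and 1-year contacts are complete, so vital status, heart failure events and health care use can be known. Some of the bases above still exclude the subject.

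**4. What would exclusion do to a rate?** Let m be the true rate, x the share excluded, and RR the risk in those excluded relative to those kept. The reported rate is m / [(1 − x) + x·RR]. The documents give none of these inputs. Assuming m = 15% and x = 20%:

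- RR 0.5: 0.15/0.9 = 16.7%
- RR 1: 0.15/1.0 = 15.0%
- RR 2: 0.15/1.2 = 12.5%
- RR 3: 0.15/1.4 = 10.7%

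The rate can rise, stay the same or fall. This shows only that the direction depends on a quantity the documents do not give.

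**The case against.** **Stopping wear is not a listed source of missing data.** Section 8.6.1 names neither stopping wear nor withdrawal, and a visit that is no longer scheduled is arguably not missed. This is fair, and on that reading the subject is kept (last row of the table). It is one reading among several, and the text does not choose between them.

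**Few subjects may be affected.** Section 7.1 expects wear above 70% and has the sponsor and sites act on early non-compliance. That bears on the number but does not bound it closely. If the 70% is a mean (an assumption), and a share p stops on day 20 while all others wear for 90 days, mean wear is 1 − p × 70/90. For assumed p of 10%, 20% or 30%, that is 92%, 84% or 77%, all above 70%.

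**Safety.** A reader might infer that subjects who stop because of a skin reaction will be removed from the safety analysis. The documents do not support that. Sections 2.3 and 3.4 point the other way, section 10 requires recording and reporting in any case, and section 3.1.1 allows a pause of up to 48 hours, or 2/90 = 2% of wear days. No rate of permanent stopping is given. What stands is a conflict between 8.6.3.2 and sections 2.3 and 3.4.

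**Deaths.** A reader might also infer that early deaths are dropped systematically and mortality is much understated. That needs time after death to count as missing. Section 8.6.1 does not list death, and chart review can supply vital status. For a death on day 40, counting only Visits 3 and 4 as missing gives 2/6 = 33%, kept. The text does not rule out the harsher count, but it is the less natural one.

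**Conclusion.** The point holds as a defect in a stated exclusion rule. Section 8.6.3.2 has no defined base, period or endpoint scope. It can exclude subjects with known outcomes from the secondary analyses, and it conflicts with sections 2.3, 3.4 and 5.4.2. The demonstration that the same subject is kept or dropped according to the base rests on document figures alone, with both late contacts assumed complete.

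The number of subjects affected, and the direction and size of any bias, cannot be determined from the documents. The rates in step 4 and the stopping shares in the objection are assumptions and not estimates. No effect on the primary correlation is claimed. This should be fixed before the analysis.

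**What to change.** 1. State that 8.6.3.2 does not apply to the readmission, heart failure event, VT/VF, mortality and safety analyses. These keep all enrolled subjects with available data, except where consent to use the data is withdrawn (section 5.4.2). Censor follow-up at last contact or chart review, and relate VT/VF to monitored time.
2. Confine any 50% rule to device data in the device-event correlation. Define its base as the scheduled initial 90 days of wear, ending at death.
3. Separately, reconcile section 3.1.1, which continues telephone calls after wear has stopped, with sections 6.2 and 6.6, which end them. This decides what is known about such subjects within the 90 days.

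The cost is a few sentences of protocol text and slightly more analysis work. Some subjects with short follow-up will enter the rates. If the third step is resolved in favour of continuing, sites make some additional calls.

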8.7 Futility Analysis

The study will be considered ineffective if the interim analysis determine the study will be unsuccessful enrolling the required number of subjects (≥ 1 subject per center-month), or if occurrence of the primary endpoint is deemed insufficient to successfully complete the study with the planned number of subjects.

Both an interim and futility analysis will be performed once the 200th subject has completed wear time. Primary and secondary endpoints will be assessed. With 200 patients completing wear time, it is expected that there would be about 25 -30 heart failure related clinical events. If during the interim and futility assessments, there are less than 5 heart failure events, a protocol change will be considered.

9 Health Economic Evaluation

The Kansas City Heart Failure Questionnaire will be given to the subjects at all monthly clinic visits. We will develop a model to examine the costs and benefits of using uCor. The model will use data from our review of monthly collected questionnaire, heart failure event, as well as data from recognized sources (e.g. national published data, finance department of hospital), and experts' advice

10 Safety and Adverse Device Effects

